12.5.1 SUBJECT REPLACEMENT

Patients who discontinue due to an (S)AE must be followed-up with appropriate clinical and/or laboratory tests until the (S)AE has resolved satisfactorily, in the opinion of the investigator.

If a patient discontinues for non-(S)AE reasons at any time after entering the study, but before receiving the first treatment, the patient will be replaced.

Patients who discontinue from study treatment within 2 months after start of study treatment for other reasons than ADR(s) will be replaced. Patients withdrawing for ADRs will NOT be replaced. Study drop-outs can be replaced if needed.

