Statistical Analyses: Descriptive analyses of efficacy and safety variables will be used. The analysis will be performed on the data collected up to the last MRD assessment (Day 224). In general, descriptive statistics, unless otherwise noted, will include the number of subjects, mean, standard deviation, median, minimum value, and maximum value, and where applicable, 95% confidence intervals. Percentages will be calculated using the number of subjects within each treatment group. If appropriate, immune monitoring data will be summarized using the geometric mean, standard error of the geometric mean, and 95% confidence intervals of the geometric mean. Time to event variables (e.g. time to relapse or change in MRD status) will be analysed using survival analysis techniques (e.g. Kaplan-Meier estimates).

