12.5 END OF TREATMENT

Study discontinuation refers to complete withdrawal from the study treatment. The reason for discontinuation from treatment must be recorded. Study discontinuation can be based on one or more of the following criteria:

- Adverse event(s) (physician's discretion)
- Disease progression
- Protocol violation
- Subject withdrew consent
- Lost to follow-up
- Administrative problems
- Death
- Treatment duration completed as per protocol

Furthermore, treatment ends when:

1. No return to baseline or no return to grade 1 non-hematological toxicity at any time during/after the vaccination.
2. Related SAE not otherwise categorized within the CTC v4.0 criteria (see Appendix B) but defined as severe or life threatening at any time during/after vaccination.

Based on the above, there is a differentiation between treatment withdrawal (withdraw treatment, but continue follow-up) and study drop-out (withdrawal from study e.g. unwillingness of the patient to comply with study procedures, withdraw consent, or lost to follow-up).

DCPrime must be notified and the reason(s) for treatment withdrawal/study drop-out should be documented in the eCRF; all follow-up data should also be reported.

Patients who have received at least one dose of DCP-001 who are withdrawn, or withdraw from the study will be treated according to protocol as EOT and EOT pages will be completed. If the patient does not withdraw informed consent, he/she will be requested to enter the follow up phase of the study. These patients will follow the normal schedule of the study excluding the injection of study treatment and the procedures at these visits will occur at the investigators' discretion. These patients will continue to be followed up until EOS or EOT of last patient who completed the study, whichever comes first

If the patients who are required to enter follow up do not enter follow up, for any reason, they must be requested to complete an EOT and EOS visit.

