16 STATISTICAL METHODS

16.1 DETERMINATION OF SAMPLE SIZE

Recruitment will target 20 patients greater than 18 years of age with a confirmed diagnosis of AML that are in CR1 or CRi with MRD. The planned sample size of 20 evaluable subjects will be distributed 1:1 with 10 subjects each in Group 1- 25E6 DCP-001 cells per vaccination, and Group 2- 50E6 DCP-001 cells per vaccination. Additional subjects may be enrolled to ensure that 20 evaluable subjects complete the study. As the impact of vaccination on MRD levels is the primary endpoint, strict sample size statistical considerations with a desired power for a pre-specified difference is not yet possible. However, assuming that 90% of patients in the overall (untreated) population will experience MRD, a sample size of 20 subjects is sufficient to detect a 22% difference between the treated group and the overall population, using a one sample, two-tailed z-test of proportion with 80% power and a 5% level of significance. No formal sample size calculations were completed for this study.

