16.2 STATISTICAL AND ANALYTICAL PLANS

No inferential analysis is planned for the study; only descriptive analyses will be used. In general, descriptive statistics, unless otherwise noted, will include the number of subjects, mean, standard deviation, median, minimum value, and maximum value, and where applicable, 95% confidence intervals. Percentages will be calculated using the number of evaluable subjects within each treatment group. If appropriate, immune monitoring data will be summarized using the geometric mean, standard error of the geometric mean, and 95% confidence intervals of the geometric mean. Unless otherwise stated, all summary tables will present descriptive statistics and/or frequency by visit for each treatment group. The analysis will be performed on the data collected up to the last MRD assessment (Day 224).

All statistical analyses and data summaries will be completed using SAS Software (version 9.2 or greater).

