16.2.1 Definition of Analysis Population

The "Safety Population" will be comprised of all subjects who provide informed consent and receive at least one vaccination. Subjects in the Safety Population will be analysed as treated.

The "Immunogenicity Population" will be comprised of all subjects who received a vaccination and for whom any follow-up immune monitoring data were recorded. This is the dataset to be used for the primary outcomes.

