16.2.2 Handling of Missing Data

No adjustments in the analysis for missing data are planned. However, missing immune monitoring data will be explored and, if significant, appropriate statistical methods may be applied to adjust for missing data.

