16.2.3 Analysis of Efficacy Variables

MRD levels and immune responses will be summarized descriptively by treatment group and visit as described above. Time to event variables (e.g. time to relapse) will be analysed using survival analysis techniques (e.g, Kaplan-Meier estimates).

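### Early relapsers are replaced before any post-baseline MRD sample is due, and MRD percentages use undefined evaluable subjects, so reported MRD leans towards benefit

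*Protocol*

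**What the plan says.** **Replacement.** Protocol 12.5.1: "Patients who discontinue from study treatment within 2 months after start of study treatment for other reasons than ADR(s) will be replaced". Withdrawals for adverse drug reactions are not replaced. Section 12.5 lists disease progression and death among the reasons for discontinuation. Section 15.1 says that worsening of the disease under treatment is not an adverse event.

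**Sampling.** Marrow for MRD is due on Days 0, 98, 140 and 224 (Table 1, section 8.10.4). For patients who have stopped vaccination, 12.5 says: "These patients will follow the normal schedule of the study excluding the injection of study treatment". The same sentence leaves the procedures at those visits to the investigators' discretion.

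**Target and denominator.** Section 16.1: "Additional subjects may be enrolled to ensure that 20 evaluable subjects complete the study". Section 16.2: "Percentages will be calculated using the number of evaluable subjects within each treatment group". The synopsis: "Percentages will be calculated using the number of subjects within each treatment group". The protocol does not define evaluable.

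**Analysis.** Section 16.2.1 defines the Immunogenicity Population by vaccination plus any follow-up immune monitoring data, and adds: "This is the dataset to be used for the primary outcomes". Section 16.2.3: "MRD levels and immune responses will be summarized descriptively by treatment group and visit as described above". Section 16.2.2: "No adjustments in the analysis for missing data are planned". The exploration that follows in 16.2.2 concerns missing immune monitoring data only. Time to relapse has its own Kaplan-Meier analysis.

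**The concern.** Relapse is the worst MRD outcome a patient in remission can have. Under these rules a patient who relapses early and stops has no MRD sample due before replacement and may never have one. Enrolment can then go on until 20 evaluable patients complete. The MRD tables would therefore describe mainly patients who did not relapse.

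The effect of vaccination on MRD is a primary objective, there is no control arm, and section 8.8 says the results will inform a Phase IIb design. Selection towards patients who did well would not be cancelled by a comparison group. A reader would also be unable to tell which denominator lies behind a percentage.

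**Working it through.** **1. The plan's own figure.** Section 16.1 compares an assumed 90% MRD rate with a rate 22 points lower (68%), using a one-sample two-sided z-test at 5% with 80% power.

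n = [1.960·√(0.90·0.10) + 0.842·√(0.68·0.32)]² / 0.22² = 19.87, rounded up to 20. Power at n = 20 is 80.2%. The figure reproduces. The problem lies in which patients supply the proportion.

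**2. Does the replacement rule cover relapse?** Progression is a reason to stop (12.5). It is not an adverse event (15.1), so it cannot be an adverse drug reaction. A stop for progression within 2 months therefore counts as another reason, and replacement is mandatory (12.5.1).

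**3. Is an MRD value due first?** The window closes at about Day 60 and the first post-baseline marrow is on Day 98. None is due. A later one is discretionary.

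**4. Effect on a percentage.** Suppose 20 patients are retained, x of them are MRD-negative, and k relapsers were replaced, none of them MRD-negative.

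- Evaluable denominator: x/20
- All-vaccinated denominator: x/(20+k)
- Ratio: (20+k)/20

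| k | Ratio | 4/20 = 20.0% becomes | 6/20 = 30.0% becomes |
|---|---|---|---|
| 2 | 1.10 | 4/22 = 18.2% | 6/22 = 27.3% |
| 4 | 1.20 | 4/24 = 16.7% | 6/24 = 25.0% |
| 6 | 1.30 | 4/26 = 15.4% | 6/26 = 23.1% |

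Percentages are planned by dose group of 10, where the ratio is (10+k)/10 with k counted in that group. Two replaced relapsers turn 3/10 = 30% into 3/12 = 25%.

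**5. A plausible range for k.** Section 8.2 gives 60-80% relapse with no time scale. Assumption: constant hazard reaching that level at 12 or 24 months, with 2 months taken as Day 60. Relapse by Day 60 is 1 − (1 − R)^(60/T), and the number vaccinated for 20 retained is 20/(1 − relapse by Day 60).

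| R | T (days) | Relapse by Day 60 | Vaccinated for 20 retained |
|---|---|---|---|
| 60% | 730 | 7.3% | 21.6, about 22 |
| 80% | 730 | 12.4% | 22.8, about 23 |
| 60% | 365 | 14.0% | 23.3, about 23 |
| 80% | 365 | 23.2% | 26.1, about 26 |

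So k is about 2 to 6, and 6/20 = 30% would be 6/22 = 27.3% down to 6/26 = 23.1%.

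**6. Effect on the 90% benchmark.** Suppose vaccination does nothing: 90% of all vaccinated patients are MRD-positive, relapsers included. The MRD-positive rate in the 20 retained is then 1 − 0.10·(20+k)/20, which is 89%, 88% and 87% for k = 2, 4 and 6. The z-test limit is 20·(0.90 − 1.960·√(0.09/20)) = 15.4. The chance of 15 or fewer MRD-positive in 20 rises from 4.3% (k = 0) to 6.1%, 8.3% and 10.8%. No test is planned, so this only illustrates the section 16.1 reasoning.

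**The case against.** Several points on the other side stand and limit the claim.

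- **Replacement deletes nobody.** A reader might infer that replaced patients leave the analysis. The protocol does not say so. The primary dataset takes any vaccinated patient with follow-up immune data, and immune blood is drawn on Day 2 (Tables 1 and 4). Section 9.2.4 keeps every vaccinated patient in the efficacy database. The loss comes from absent MRD samples and from the percentage denominator.
- **Evaluable governs percentages only.** By-visit MRD levels are summarised in whoever was sampled.
- **An early relapser may still be sampled.** An untreated relapser sampled on Day 98 would raise by-visit MRD. A patient sampled after new therapy could lower it. Because sampling is discretionary, neither a total absence of values nor routine pooling can be asserted.
- **Relapse is not ignored.** It appears in the time-to-relapse analysis. The gap is in the MRD summaries.
- **Change from baseline is already a criterion.** The synopsis lists it, and within-patient change is less exposed to selection than raw by-visit levels.
- **Much larger inflation is not supported.** A reader might project relapse to Day 224 and assume enrolment until 20 patients are relapse-free then. Mandatory replacement stops at 2 months, later replacement of drop-outs is optional, and section 16.1 says evaluable completers, not relapse-free ones.

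It can also be said that the SAP will settle the details and that the study is descriptive. Neither disposes of the point. The protocol already fixes the replacement rule, two different denominators and no missing-data adjustment, and a SAP that followed it would inherit all three. A selected percentage misleads with or without a p-value.

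**Conclusion.** The point holds for MRD percentages and by-visit MRD levels. Followed as written, they describe mainly patients who did not relapse, and nothing in an uncontrolled design corrects for it. For percentages the direction is towards benefit, provided relapsers are not MRD-negative. For by-visit levels it is towards benefit if patients with higher MRD relapse more often and are then mostly unsampled.

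The inflation factor (20+k)/20 is exact given k. The value of k is not in the protocol. The range of about 22 to 26 vaccinated for 20 retained, and hence 30% against about 23-27%, rests on the assumed time scale and constant hazard, and on the 6/20 result, which is hypothetical. The conflict between the synopsis and 16.2 on the denominator needs no assumption. The rule should be settled before MRD results are summarised.

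**What to change.** 1. In 16.2 and the synopsis, use one denominator for MRD percentages: all vaccinated patients in the dose group. State there, with a cross-reference in 12.5.1, that vaccinated patients who are replaced stay in it. The replacement rule itself need not change.
2. In 16.2.3, count relapse, death or start of new anti-leukaemic therapy before an MRD visit as not MRD-negative at that and later visits, and give it the worst rank when MRD is treated as continuous. Do not use MRD values obtained after new therapy as response. This is an analysis rule and leaves patient care untouched.
3. Show within-patient log10 change from Day 0 beside the by-visit levels, in line with the synopsis criterion, with the number sampled and the reasons for missing samples at each visit.
4. Define evaluable, and keep an evaluable-only table as supportive.

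The cost is amended wording in three places, a few extra tables and a less favourable MRD percentage. No further patients or samples are needed.

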12.6 PRIOR AND CONCOMITANT THERAPY

All prior and concomitant medications/therapies will be collected from 28 days before the screening visit and throughout the study, and will be recorded in the eCRF. The exclusion criteria list the prior and concomitant medications/therapies that affect study eligibility.

Throughout the study, all medications deemed necessary for the patient's welfare and are not expected to interfere with the evaluation of the study drug may be administered at the investigators' discretion. If investigators have any questions regarding the suitability of a particular concomitant medication, the Coordinating Investigator should be contacted.

Concomitant therapy with other investigational drugs is forbidden. No immunosuppressive treatment may be offered such as cyclosporine, cyclophosphamide, methotrexate and others except for short use of low dose prednisone (up to a maximum of 10mg/day or other corticosteroid equivalent dose) if indicated for example for concomitant dermal diseases such as Sweet syndrome and/or eczema.

12.7 BIRTH CONTROL METHODS

Patients who are able to become pregnant during the study period should be advised to use appropriate contraception methods. As highly effective birth control methods the following are to be advised:

- Combined (estrogen and progestogen) containing hormonal contraception (oral, intravaginal or transdermal)
- Progestogen-only hormonal contraception (oral, injectable or implantable)
- Intrauterine device (IUD)
- Intrauterine hormone-releasing system (IUS)
- Bilateral tubal occlusion
- Vasectomized partner
- Sexual abstinence

13 STUDY DRUG MANAGEMENT

13.1 PACKAGING AND LABELLING

The investigational drug product DCP-001 will be manufactured at Apceth GmbH, a qualified licensed manufacturer specialized in production of cell therapeutic products. Manufacturing records and certificate of analysis will be issued for all batches to allow release and certification by a Qualified Person (QP). Release by the QP will be performed in accordance with Good Manufacturing Practice (GMP) guidelines, ICH GCP guidelines and applicable local laws/regulations.

DCP-001 is presented as a direct injectable solution containing a dendritic cell preparation suspended in Cryostor™ and stored frozen at $\leq -135^{\circ}\text{C}$. The vaccine is packed in Daiko Crystal Zenith vials. These vials are USP Class VI vials, Sterile (SAL 10-6) according to ISO 11137. The vial format is based on the traditional glass vial with a rubber stopper and aluminium crimp seal with flip-off cap. This will allow easy and sterile bedside handling of the injectable DCP-001.

Sample Label:

| | |
|--|---|
| DCP-001 | 1,25 ml Cell concentration see COA Zellkonzentration siehe Analysenzertifikat |
| Sponsor: DCPrime BV, [name] | Advance II Study |
| CRO: Lincal Accelovance, xxxxxxxxxxxx, xxxxxxxxxxxx | EudraCT-Nr.: 2017-002869-22 |
| Cell suspension for intradermal application | Zellsuspension zur intradermalen Anwendung |
| For clinical trial use only | Nur zur klinischen Prüfung |
| Store at / Lagerung bei $\leq -135^{\circ}\text{C}$ | Lot/Ch.-B.: DC000XX Exp / Verwendbar bis: MM JJJJ |

13.2 STUDY DRUG HANDLING AND STORAGE

Upon receipt at the clinical site, the DCP-001 vials should be immediately transferred to a $\leq -135^{\circ}\text{C}$ freezer. At the time of vaccination, the vials are removed from the freezer, placed on dry ice, thawed in a 37° water bath according to written procedures, and drawn into the labelled syringes. The syringes are then placed on wet ice, or in a refrigerated box, and released to the appropriated personnel for intradermal injection. Primed syringes must be kept on wet ice or in a refrigerated box until immediately before the vaccine is administered. All injections must be given within 60 min of end of thaw cycle.

13.3 RESPONSIBILITIES FOR STUDY DRUG(S)

Current ICH GCP guidelines require the investigator to ensure that study medication deliveries from the sponsor are received by a responsible person (e.g. a pharmacist), and

- that such deliveries are recorded
- that study medication is handled and stored safely and in accordance with the pharmacy manual
- that study medication is only dispensed to study patients in accordance with the protocol
- that any unused study medication is to be returned to the sponsor.

Drug inventory and accountability records for the medication in this study will be kept by the pharmacist. The following guidelines are therefore pertinent:

- The investigator agrees not to supply study medication to any person except the patients in this study.
- The pharmacist will keep the study drugs in a pharmacy or other locked and secure storage facility, accessible only to those authorized by the investigator to dispense these investigational drugs.
- A study medication inventory will be maintained by the pharmacist. The inventory will include details of materials received and a clear record of when they were dispensed and to which patient.
- At the conclusion or termination of this study, the pharmacist agrees to conduct a final drug supply inventory and to record the results of this inventory on the Drug Accountability Record.
- Unused study medication or medication not dispensed will be returned to the sponsor. It must be possible to reconcile delivery records with those of used and returned medication. Account must be given for any discrepancies. Certificates of deliveries and returns must be signed by the responsible person and made available to the Sponsor, or their representative.

The procedures to ensure appropriate storage, handling and accounting of study medication, will be presented in the Pharmacy Manual supplied to each clinical centre pharmacist or delegate.

As this study involves intradermal administration of the study medication administered by trained study personnel, patient compliance measures are not necessary. Study medication will be administered under direct supervision, according to the Pharmacy Manual and the clinical centre's standard operating procedures.

14 STUDY PROCEDURES

14.1 STUDY PROCEDURES AT EACH VISIT

Patients will be screened for eligibility to participate in the study within 4 weeks prior to the first vaccination.

Visit 1 (Screening Visit)

Screening assessments will include:

- Obtaining of written informed consent prior to any study specific procedure (including screening procedures) being performed
- Verify all inclusion criteria are met and no exclusion criteria are met
- Record demographics
- Complete medical history; including previous therapies for AML
- Perform physical examination assessment. The physical examination of baseline will also include WHO Performance status (ECOG)
- Record vital signs (heart rate, blood pressure and oral body temperature)
- Urine analysis
- Perform study specific haematology and biochemistry (incl. beta hCG blood test in woman with child bearing potential)
- Viral screen (HIV, Hepatitis B and C)
- ECG, X-thorax
- HLA typing
- Record any prior and concomitant medications

All laboratory procedures (including central laboratory) will be described in the Laboratory manual.

Treatment Period; Visit 2 (Baseline Visit)/ day 0

The Baseline Visit will include:

- Physical examination, ECOG and Vital signs
- Perform study specific hematology and biochemistry
- Record any new AEs, SAEs and concomitant medications and/or changes in ongoing AEs, SAEs and ongoing concomitant medications
- Blood sample collection for immunological response (immunomonitoring) before vaccination
- Administration of study medication (DCP-001 vaccination)
- Bone marrow aspirate for MRD analysis (MRD assessment) and biobanking

Treatment Period (Visit 3)/ day 2

- Skin biopsy from 1 out of the 2 or 4 injection sites for evaluation of immunological response in skin biopsy
- Blood sample collection for immunological response
- Record new any AEs, SAEs and concomitant medications and/or changes in ongoing AEs,

SAEs and ongoing concomitant medications

- Day is fixed with the previous visit (Visit 2)

Treatment Period (Visit 4-6)/days 14, 28 and 42

The following assessments will be performed at the indicated visits according to the assessment schedule \pm 3 days.

- Physical examination, ECOG and Vital signs
- Hematology and biochemistry
- Record any AEs, SAEs and concomitant medications and/or changes in ongoing AEs, SAEs and ongoing concomitant medications.
- Administration of study medication (DCP-001 vaccination)

Treatment Period (Visit 7)/ day 44

- Skin biopsy from 1 out of the 2 or 4 injection sites for evaluation of immunological response in skin biopsy.
- Blood sample collection for immunological response
- Record any AEs, SAEs and concomitant medications and/or changes in ongoing AEs, SAEs and ongoing concomitant medications
- Day is fixed with the previous visit (Visit 6)

Treatment Period (Visit 8)/ day 77

according to the assessment schedule \pm 3 days

- Physical examination, ECOG and Vital signs
- Record any new AEs, SAEs and concomitant medications and/or changes in ongoing AEs, SAEs and ongoing concomitant medications
- Blood sample collection for immunological response

Treatment Period (Visit 9-10)/days 98, 126

according to the assessment schedule \pm 3 days

- Physical examination, ECOG and Vital signs
- Hematology and biochemistry
- Record any new AEs, SAEs and concomitant medications and/or changes in ongoing AEs, SAEs and ongoing concomitant medications.
- Administration of study medication (DCP-001 booster vaccination)
- **Visit 9;** Bone marrow aspirate for MRD analysis (MRD assessment) and biobanking

Treatment Period (Visit 11)/day 128

- Skin biopsy from 1 out of the 2 or 4 injection sites for evaluation of immunological response in skin biopsy
- Blood sample collection for immunological response (immunomonitoring)
- Record any new AEs, SAEs and concomitant medications and/or changes in ongoing AEs, SAEs and ongoing concomitant medications
- Day is fixed with the previous visit (visit 10)

Treatment Period (Visit 12)/day 140

according to the assessment schedule \pm 3 days

- Physical examination, ECOG and Vital signs
- Hematology and biochemistry
- Record any AEs, SAEs and concomitant medications and/or changes in ongoing AEs, SAEs and ongoing concomitant medications.
- Bone marrow aspirate for MRD analysis (MRD assessment) and biobanking
- Blood sample collection for immunological response (immunomonitoring)

Treatment Period (Visit 13)/ day 224

according to the assessment schedule \pm 3 days

- Physical examination, ECOG and Vital signs
- Hematology and biochemistry
- Record any new AEs, SAEs and concomitant medications and/or changes in ongoing AEs, SAEs and ongoing concomitant medications.
- Bone marrow aspirate for MRD analysis (MRD assessment) and biobanking
- Blood sample collection for immunological response

Follow-up visits (14-17)

Upon completion of the treatment phase each patient will enter the follow up phase. The patient will return every 8 weeks (\pm 2 weeks) up to 12 months after 4th vaccination. The following assessments will be performed at each follow up visit;

- Physical examination, ECOG and Vital signs
- Hematology and biochemistry
- Record any new AEs, SAEs and concomitant medications and/or changes in ongoing AEs, SAEs and ongoing concomitant medications

Subsequent follow up visits will occur at least every 8 ± 2 weeks until end of study (i.e. 12 months after 4th vaccination) or disease progression.

End of study visit (18) / 12 months after last vaccination

- Physical examination, ECOG and Vital signs
- Perform study specific hematology and biochemistry
- Urine analysis
- Record any new AEs, SAEs and concomitant medications and/or changes in ongoing AEs, SAEs and ongoing concomitant medications

See schedule of assessment (Table 1) for study specific procedures.

